12.8.2 Secondary endpoint(s)

The tests of the key secondary endpoint are not used for sample size calculation. These tests are similar to the five tests of each primary endpoint and will be performed after the tests of primary endpoints succeed.

13 Ethical considerations and administrative procedures

13.1 Regulatory and ethical compliance

This clinical study was designed and shall be implemented, executed and reported in accordance with the International Council for Harmonization (ICH) Harmonized Tripartite Guidelines for Good Clinical Practice, with applicable local regulations (including European Directive 2001/20/EC, US CFR 21), and with the ethical principles laid down in the Declaration of Helsinki.

13.2 Responsibilities of the investigator and IRB/IEC

Before initiating a trial, the investigator/institution must obtain approval/favorable opinion from the Institutional Review Board/Independent Ethics Committee (IRB/IEC) for the trial protocol, written informed consent form, consent form updates, participant recruitment procedures (e.g. advertisements) and any other written information to be provided to participants. Prior to study start, the investigator is required to sign a protocol signature page confirming his/her agreement to conduct the study in accordance with these documents and all of the instructions and procedures found in this protocol and to give access to all relevant data and records to Novartis monitors, auditors, Novartis Quality Assurance representatives, designated agents of Novartis, IRBs/IECs, and regulatory authorities as required. If an inspection of the clinical site is requested by a regulatory authority, the investigator must inform Novartis immediately that this request has been made.

13.3 Publication of study protocol and results

The protocol will be registered in a publicly accessible database such as clinicaltrials.gov and as required in EudraCT. In addition, after study completion (defined as last participant last visit) and finalization of the study report the results of this trial will be submitted for publication and posted in a publicly accessible database of clinical trial results, such as the Novartis clinical trial results website and all required Health Authority websites (e.g. Clinicaltrials.gov, EudraCT etc.).

For details on the Novartis publication policy including authorship criteria, please refer to the Novartis publication policy training materials that were provided to you at the trial investigator meetings.

13.4 Quality Control and Quality Assurance

Novartis maintains a robust Quality Management System (QMS) that includes all activities involved in quality assurance and quality control, to ensure compliance with written Standard Operating Procedures as well as applicable global/local GCP regulations and ICH Guidelines.

Audits of investigator sites, vendors, and Novartis systems are performed by auditors, independent from those involved in conducting, monitoring or performing quality control of the clinical trial. The clinical audit process uses a knowledge/risk based approach.

Audits are conducted to assess GCP compliance with global and local regulatory requirements, protocols and internal Standard Operating Procedures (SOPs), and are performed according to written Novartis processes.

14 **Protocol adherence**

This protocol defines the study objectives, the study procedures and the data to be collected on study participants. Additional assessments required to ensure safety of participants should be administered as deemed necessary on a case by case basis. Under no circumstances including incidental collection is an investigator allowed to collect additional data or conduct any additional procedures for any purpose involving any investigational drugs under the protocol, other than the purpose of the study. If despite this interdiction prohibition, data, information, observation would be incidentally collected, the investigator shall immediately disclose it to Novartis and not use it for any purpose other than the study, except for the appropriate monitoring on study participants.

Investigators ascertain they will apply due diligence to avoid protocol deviations. If an investigator feels a protocol deviation would improve the conduct of the study this must be considered a protocol amendment, and unless such an amendment is agreed upon by Novartis and approved by the IRB/IEC and Health Authorities, where required, it cannot be implemented.

14.1 **Protocol amendments**

Any change or addition to the protocol can only be made in a written protocol amendment that must be approved by Novartis, health authorities where required, and the IRB/IEC prior to implementation.

Only amendments that are required for participant safety may be implemented immediately provided the health authorities are subsequently notified by protocol amendment and the reviewing IRB/IEC is notified.

16.1 Appendix 1: Clinically notable laboratory values and vital signs

The central laboratory will flag laboratory values falling outside of the normal ranges on the central laboratory reports. Investigators are responsible for reviewing these abnormal values for clinical significance, signing the laboratory reports to indicate their review, and reporting values considered clinically significant in the appropriate eCRF. Any clinically significant abnormal laboratory value should be evaluated and followed-up by the investigator until normal or a cause for the abnormality is determined.

SEE APPENDIX 16.2 FOR SPECIFIC LIVER EVENT AND LABORATORY TEST TRIGGER DEFINITIONS AND FOLLOW-UP REQUIREMENTS.

For ECGs, a notable QTc value is defined as a QTcF (Fridericia) interval of \geq 450 msec for males or \geq 460 msec for females, all such ECGs will be flagged by the Central CRO and require assessment for clinical relevance and continuance of the participant by the Investigator.

For vital signs, please see Table 16-1 for notable abnormalities.

Vital signs		Nota	Notable abnormalities		
	Absolute		Relative to baseline		
Pulse rate (beats/min)	> 130 < 40	> 120 and increase from baseline ≥ 15		
			≤ 50 and decrease from baseline ≥ 15		
Blood pressure (mmHg)	Systolic	> 200 < 75	\geq 180 and increase from baseline \geq 20		
			≤ 90 and decrease from baseline ≥ 20		
	Diastolic	> 115 < 40	≥ 105 and increase from baseline ≥ 15		
			≤ 50 and decrease from baseline ≥ 15		

Table 16-1 Vital signs

Note: these notable ranges should not be used as reference ranges to establish a clinical diagnosis

16.2 Appendix 2: Liver event and Laboratory trigger Definitions and Follow-up Requirements

Confidential

Table 16-2 describes detailed thresholds and actions needed when elevations of liver parameters is observed or symptoms / adverse events indicative of liver toxicity appear. These symptoms could include jaundice, clinical evidence of liver decompensation, histology findings suggestive of drug induced liver injury or development of benign or malignant liver neoplasms.

For transaminases (ALT, AST), GGT, ALP, DBL and TBL, the baseline value will be calculated as the mean of the assessments before first administration of the study drug, which are those taken at the Screening and Baseline visits.

For normal reference ranges for AST, ALT, GGT, TBL and ALP, please refer to the values provided by the Central Laboratory.

Table 16-2Management of Participants with Confirmed ALP, ALT, AST, or
Bilirubin Elevations With or Without Liver Related Clinical Symptoms

Baseline	Treatment-Emergent	Liver-	Action	taken
	(Confirmed ^a)	Related Clinical Symptoms ^b	Monitoring ^c	Study Drug
ALT and/or AST				
Baseline ALT and/or AST < 2 × ULN	ALT and/or AST > 3 × ULN but ≤ 5 × baseline	None	Laboratory monitoring and causality evaluation	Continue dosing
		Present	Comprehensive clinical evaluation and laboratory monitoring, as well as causality evaluation ^d ,	Interrupt dosing ^e
	ALT and/or AST > 3 × ULN but ≤ 5 × baseline AND total bilirubin > 2 × ULN (in Gilbert's syndrome, see footnote ^f)	With or without liver-related clinical symptoms	Comprehensive clinical evaluation and laboratory monitoring, as well as causality evaluation ^d ,	Interrupt dosing ^e
	ALT and/or AST > 3 × ULN and > 5 × baseline	With or without liver-related clinical symptoms	Comprehensive clinical evaluation and laboratory monitoring, as well as causality evaluation ^d ,	Permanently discontinue

Novartis	Confidential	
Amended Protocol Version 02 (Clean)		Protocol No. Cl

Amended Protocol Ve	ersion 02 (Clean)	Protocol No.	CLJN452D12201C		
Baseline	Treatment-Emergent	Liver-	Action taken		
	(Confirmed ^a)	Related Clinical Symptoms ^b	Monitoring ^c	Study Drug	
Baseline ALT and/or AST ≥ 2 × ULN	ALT and/or AST > 2 × baseline but ≤ 3 × baseline	None	Laboratory monitoring and causality evaluation	Continue dosing	
		Present	Comprehensive clinical evaluation and laboratory monitoring, as well as causality evaluation ^d ,	Interrupt dosing ^e	
	ALT and/or AST > 2 × baseline but ≤ 3 × baseline AND total bilirubin > 2 × ULN ^f	With or without liver-related clinical symptoms	Comprehensive clinical evaluation and laboratory monitoring, as well as causality evaluation ^d ,	Interrupt dosing ^e	
	ALT and/or AST > 3 × baseline	With or without liver-related clinical symptoms	Comprehensive clinical evaluation and laboratory monitoring, as well as causality evaluation ^d ,	Permanently discontinue	
Baseline normal or elevated ALT and/or AST values	ALT and/or AST > 3 × ULN and > 2 × baseline AND either total bilirubin > 2 × baseline OR INR increase by >0.3 to a value >1.5	With or without liver-related clinical symptoms	Comprehensive clinical evaluation and laboratory monitoring, as well as causality evaluation ^d ,	Interrupt dosing ^e	
ALP					
Baseline ALP ≤ ULN	ALP > 1.5 × ULN (not due to known bone pathology)	None	Laboratory monitoring and causality evaluation ^c	Continue dosing	
		Present	Comprehensive clinical evaluation and laboratory monitoring, as	Interrupt dosing ^e	

Novartis	Confidential	Page 154 of 160
Amended Protocol Version 02 (Clean)		Protocol No. CLJN452D12201C

Novartis	Confidential		Page 154 of 1		
Amended Protocol Ve				CLJN452D12201C	
Baseline	Treatment-Emergent (Confirmedª)	Liver- Related Clinical Symptoms ^b	Action Monitoring ^c	taken Study Drug	
			well as causality evaluation ^d ,		
	ALP > 1.5 × ULN (not due to known bone pathology) AND total bilirubin > 2 × ULN ^f	With or without liver-related clinical symptoms	Comprehensive clinical evaluation and laboratory monitoring, as well as causality evaluation ^d ,	Interrupt dosing ^e	
Baseline ALP > ULN	ALP > 2 × baseline (not due to known bone pathology)	None	Laboratory monitoring and causality evaluation ^c	Continue dosing	
		Present	Comprehensive clinical evaluation and laboratory monitoring, as well as causality evaluation ^d ,	Interrupt dosing ^e	
	ALP > 2 × baseline (not due to known bone pathology) AND total bilirubin > 2 × ULN ^f	With or without liver-related clinical symptoms	Comprehensive clinical evaluation and laboratory monitoring, as well as causality evaluation ^d ,	Interrupt dosing ^e	
Total or Direct Bilin	ubin		 	•	
Baseline total bilirubin ≤ ULN	Total bilirubin > 2 × ULN ^f	With or without liver-related clinical symptoms	Comprehensive clinical evaluation and laboratory monitoring ^c , as well as causality evaluation ^d ,	Interrupt dosing ^e	
Baseline total bilirubin > ULN	Total bilirubin > 1.5 × baseline ^f	With or without liver-related clinical symptoms	Comprehensive clinical evaluation and laboratory monitoring ^c , as well as causality evaluation ^d ,	Interrupt dosing ^e	

Novartis Amended Protocol Ve	vartis Confidential nended Protocol Version 02 (Clean)		Page 155 of 160 Protocol No. CLJN452D12201C	
Baseline	Treatment-Emergent	Liver-	Action	
	(Confirmed ^a)	Related Clinical Symptoms ^b	Monitoring ^c	Study Drug
Baseline normal or elevated direct bilirubin	Direct bilirubin > 1.5 mg/dL	With or without liver-related clinical symptoms	Comprehensive clinical evaluation and laboratory monitoring ^c , as well as causality evaluation ^d ,	Interrupt dosing ^e
ALT, AST, ALP and	Total Bilirubin	1	1	+
Baseline normal	Normal or elevated values	Present	Comprehensive clinical evaluation and laboratory monitoring ^c , as well as causality evaluation ^d ,	Continue or Interrupt dosing as appropriate ^g
	Potential DILI cases defined as ALT or AST > 3 × ULN and TBL > 2 × ULN	With or without liver-related clinical symptoms	Comprehensive clinical evaluation and laboratory monitoring ^c , as well as causality evaluation ^d , (Refer Section 10.2.1 for required investigations)	Interrupt dosing ^e
Baseline elevated	Potential DILI cases defined as [AST or ALT > 2 x baseline] OR [AST or ALT >7 × ULN] whichever occurs first combined with [total bilirubin > 2 x baseline AND > 2.0 x ULN]	With or without liver-related clinical symptoms	Comprehensive clinical evaluation and laboratory monitoring ^c , as well as causality evaluation ^d , (Refer Section 10.2.1 for required investigations)	Interrupt dosing ^e
eCRF = electronic ULN = upper limit ^a The required con	bsphatase; ALT = alanine ar case report form; INR = inte of normal firmatory measurement sho	ernational norm uld be obtained	e; AST = aspartate a alized ratio; d within 48 to 72 hou	; urs after the

^a The required confirmatory measurement should be obtained within 48 to 72 hours after the laboratory results become available. If prompt evaluation is not possible, study drug should be interrupted immediately (date of last study drug dose must be recorded in the eCRF).
 ^b Combination of clinical symptoms of abdominal pain, worsening or new fatigue, anorexia, provide the evaluation of clinical symptoms of abdominal pain, worsening or new fatigue, anorexia,

nausea, rash, vomiting, diarrhea, fever, pruritus, and/or eosinophilia (> 5%). ^c Frequent hepatic laboratory testing and clinical assessments, including a thorough causality evaluation, should be performed every other week at minimum, in consultation with the sponsor,

lovartis Amended Protocol Ve	Confidential ersion 02 (Clean)		Page 156 of 16 Protocol No. CLJN452D12201	
Baseline	(Confirmed ^a) Related Clinical	Liver-	Action taken	
			Monitoring ^c	Study Drug
until resolution of clinical symptoms and/or stabilization of liver biochemistries to baseline levels or baseline grade of abnormality. Also, see Section 10.2 for suggested investigations particularly for Potential Hy's law. ^d The sponsor should be notified of laboratory abnormalities and any clinical symptoms, and participants should be closely monitored until resolution of clinical symptoms/stabilization of liver biochemistries to baseline levels or baseline grade of abnormality. ^e Study drug must be interrupted (date of last study drug dose must be recorded in the eCRF). The sponsor should be notified of laboratory abnormalities and any clinical symptoms, and participants should be closely monitored until resolution of clinical symptoms/stabilization of liver biochemistries to baseline levels or baseline grade of abnormality. In participants with elevations in liver biochemistry but who do not meet permanent drug discontinuation criteria, study drug may be resumed if it is determined that complete resolution to normal or clinically comparable to baseline levels or baseline grade of abnormality (baseline value will be calculated as the mean of the assessments before first administration of the study drug, which are those taken at the screening and baseline visit) has occurred and it is not considered that the deterioration in liver function was related to study drug. This must be documented based on biochemical parameters and clinical symptoms, per the discretion of the investigator and in consultation with the sponsor. If significant liver abnormalities recur at any time after restarting study drug, then study drug must be permanently discontinued. ^g Development of liver-related clinical symptoms in absence of biochemical abnormalities is an indication for prompt biochemical and physical evaluation to decide whether continued dosing is appropriate. If prompt evaluation is not possible, study drug should be interrupted and participant followed for laboratory monitoring and causality evaluation.				

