5.2 Exclusion criteria

Participants meeting any of the following criteria are not eligible for inclusion in this study.

- 1. Taking medications prohibited by the protocol. (see Section 6.2.2, Table 6-3)
- 2. Pregnant or nursing (lactating) women.
- 3. Weight at Baseline changed by > 5% since qualifying liver biopsy.
- 4. History of hypersensitivity to either of the study drugs or their excipients or to drugs of similar chemical classes, or participants with hereditary galactose intolerance, lactase deficiency or glucose-galactose malabsorption.
- 5. Taking a permitted medication listed in Table 6-2 but who is NOT on a stable dose (within 25% of Baseline dose) from the start of the screening period and
 - a. for at least 3 months prior to the Baseline visit for thyroid hormone, oral antidiabetic medication, insulin, GLP-1 agonists, and estrogen or estrogen containing birth control
 - b. for at least 6 months prior to Baseline for Vitamin E
- 6. Current, or history of, significant alcohol consumption for a period of more than 3 consecutive months within 1 year prior to screening.
 - a. Significant alcohol consumption is defined as more than 20 g/day (14 units/week) in females, or more than 30 g/day (21 units/week) in males, on

Novartis	Confidential	Page 73 of 160
Amended Protocol Version 02 (Clean)		Protocol No. CLJN452D12201C

average. A "unit" of alcohol is equivalent to one (12-ounce; 355 ml) beer, one glass (4-ounce; 120 ml) of wine, or 1 shot (ounce; 30 ml) of hard liquor.

or

- b. A score on the alcohol use disorders identification test (AUDIT) questionnaire ≥ 8 .
- 7. Diabetes related:
 - a. Type 1 diabetes mellitus.
 - b. Uncontrolled type 2 diabetes defined as $HbA1c \ge 9.0\%$ at screening.
 - c. HbA1c < 6.5% at screening in Type 2 diabetics currently treated with insulin or sulfonylureas.
- 8. Platelet count < LLN (see Central laboratory manual).
- 9. Clinical evidence of liver impairment as defined by the presence of any of the following abnormalities:
 - a. Serum albumin < LLN (see Central laboratory manual).
 - b. International Normalized Ratio (INR) > ULN (see Central laboratory manual).
 - c. ALT or $AST > 5 \times ULN$ (in either of the 2 values during screening).
 - d. Total bilirubin > ULN (see Central laboratory manual) (in either of the 2 values during screening), including Gilbert's syndrome.
 - e. Alkaline phosphatase > 300 IU/L (in either of the 2 values during screening).

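### Table 16-2 places participants whose baseline ALT and AST straddle 2 × ULN in both strata, so one confirmed result can call for both continuing and permanently stopping study drug

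*Protocol*

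**What the plan says.** Protocol Section 16.2, Table 16-2, governs confirmed rises in ALT and AST. It has two baseline strata.

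- Lower stratum, "Baseline ALT and/or AST < 2 × ULN". A participant without liver symptoms continues dosing at "ALT and/or AST > 3 × ULN but ≤ 5 × baseline". Study drug is stopped permanently at "ALT and/or AST > 3 × ULN and > 5 × baseline", with or without symptoms.
- Upper stratum, "Baseline ALT and/or AST ≥ 2 × ULN". A participant without symptoms continues dosing at "ALT and/or AST > 2 × baseline but ≤ 3 × baseline". Study drug is stopped permanently at "ALT and/or AST > 3 × baseline", with or without symptoms.

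Other rows, triggered by bilirubin or INR, lead to interruption and are not at issue here. For the transaminases, "the baseline value will be calculated as the mean of the assessments before first administration of the study drug", drawn from the screening and baseline visits. Section 5.2 excludes ALT or AST above 5 × ULN ("in either of the 2 values during screening"), so values up to that level may enter and both strata can be populated.

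Section 9.1.1 requires discontinuation for liver-test elevations that mandate it, and sends the reader to Sections 10.2.1 and 16.2 to learn which those are. Section 10.2.1 sends the reader to Table 16-2.

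**The concern.** The two stratum headings look complementary, but they are so only for one enzyme at a time. With two enzymes joined by and/or, a participant with one below and one at or above 2 × ULN satisfies both headings. The rows beneath carry different multiples of baseline, so the same confirmed result can fall in a continue row of one stratum and a permanent-stop row of the other.

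A stopping rule should give one answer per result. If it does not, two sites could each follow the table and act differently on the same laboratory report. The action can also reach the primary analysis. Under Sections 2.1 and 12.4.3, premature discontinuation before Week 24 makes the participant a non-responder, whereas after Week 24 the Week 48 biopsy is still sought and used.

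**Working it through.** The plan states no figure to reproduce here. The check applies the rows to specific values.

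**Inputs** (all from Table 16-2, in × ULN). Let b be the baseline of the enzyme that rises and x its confirmed on-treatment value. Assume no symptoms, bilirubin and INR rows not triggered, and the other enzyme unchanged.

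- Lower stratum, continue: 3 < x ≤ 5b
- Lower stratum, permanent stop: x > 3 and x > 5b
- Upper stratum, continue: 2b < x ≤ 3b
- Upper stratum, permanent stop: x > 3b

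**One enzyme alone.** A baseline is either below 2 or at least 2, so only one stratum applies. A scan of b from 0.2 to 5 and x from 0.1 to 20 found no point matching both actions.

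**Two enzymes straddling 2 × ULN.** Both headings are met. A lower-stratum continue and an upper-stratum stop coincide when x is above both 3 and 3b but no more than 5b.

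| Baseline ALT / AST | Confirmed ALT | Lower stratum | Upper stratum |
|---|---|---|---|
| 2.5 / 1.5 | 8.0 | 8.0 ≤ 5 × 2.5 = 12.5: continue | 8.0 > 3 × 2.5 = 7.5: stop permanently |
| 1.5 / 2.5 | 6.0 | 6.0 ≤ 5 × 1.5 = 7.5: continue | 6.0 > 3 × 1.5 = 4.5: stop permanently |
| 1.9 / 2.1 | 7.0 | 7.0 ≤ 5 × 1.9 = 9.5: continue | 7.0 > 3 × 1.9 = 5.7: stop permanently |

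**Is there a tie-break?** Two can be inferred. Neither is written down.

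- The enzyme that rises also sets the stratum. Row 1 then gives stop; rows 2 and 3 give continue.
- Any row that mandates stopping prevails, by way of Section 9.1.1. All three rows then give stop.

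The two readings agree on row 1 and disagree on rows 2 and 3, so a reader cannot recover a single action by inference.

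**Secondary check: the limit across the cut.** For one enzyme, the permanent-stop limit is the larger of 3 and 5b when b < 2, and 3b when b ≥ 2.

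| Baseline b | 1.9 | 1.99 | 2.0 | 2.5 | 3.0 | 3.33 |
|---|---|---|---|---|---|---|
| Limit | 9.5 | 9.95 | 6.0 | 7.5 | 9.0 | 9.99 |

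The limit regains 10 × ULN at b = 10/3. A confirmed, symptom-free value of 7, 8 or 9 × ULN means continue at a baseline of 1.9 and stop permanently at 2.0.

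**The case against.** The strongest reply is that no sensible reader would enter the lower stratum through AST and then apply its multiple to ALT. A test against baseline naturally uses one enzyme throughout, and Section 10.2.1 asks for elevations to be read against the participant's own baseline. On that reading the overlap disappears. This is a fair account of what may have been meant, but the table does not say it.

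A second reply is that Section 9.1.1 already decides the matter, because a mandated stop is required whatever another row says. That is arguable. But Section 9.1.1 defines a mandated stop by pointing to the same table, and it does not say that one row overrides another.

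Third, there are safeguards. Rises must be confirmed, the sponsor must be told within 48 hours, the investigator must stop treatment believed to be harmful, and a DMC reviews laboratory safety. These stand, and they lower the chance that sites diverge. They do not make the table consistent.

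Fourth, a reader might infer that the drop in the limit at 2 × ULN is itself an error. The documents do not support that. A rule with smaller multiples at higher baselines will step at its cut, and each single-enzyme value still gets one action. The log for Amendment 01 says the table was aligned with Health Authority recommendations used in the sponsor's other NASH studies. The step therefore warrants only a query.

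**Conclusion.** The conflict is real on the wording as it stands. It arises only when baseline ALT and AST lie on opposite sides of 2 × ULN and the confirmed rise falls in the band above 3 × ULN and 3 × baseline, up to 5 × baseline, without symptoms and without a bilirubin or INR trigger. For a rising enzyme with a baseline of 2.5 × ULN, that band runs from above 7.5 to 12.5 × ULN. The documents do not show how many participants would be affected.

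Three stronger inferences are not supported.

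- That the rows contradict each other for one enzyme: they do not. The cause is the and/or wording, not the cut-point.
- That the reported count of liver events is distorted: SAP Section 2.8.1.1 counts events identified under protocol Section 16.2, not dosing actions. The first example meets a trigger row in either stratum and is counted either way.
- That this is the trial's principal stopping rule: Section 9.1.1 lists it among several.

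The finding assumes that no footnote settles the choice of stratum. The text of footnote f is not in the copy reviewed, but the table attaches that footnote to bilirubin conditions.

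**What to change.** The sponsor should reconcile the ALT/AST rows of Table 16-2 with each other and with Section 9.1.1, so that every confirmed result leads to one action, including when baseline ALT and AST fall on opposite sides of 2 × ULN. The clarification should then go to sites.

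As a secondary query, the sponsor's safety leads should confirm that the fall in the absolute permanent-stop limit, from just under 10 to 6 × ULN at a baseline of 2 × ULN, is intended. No threshold or governing rule is proposed here; both are for the sponsor's clinical leads.

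The cost is table wording in the next amendment and a site memo. No new visits, tests or analyses are needed. Amendment 02 already revised this table once.
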